### **BASIC RESEARCH ARM**

- 13) Concomitant with the clinical arm of the study, a basic research arm will be performed to analyze the tumor specimens using histologic, immunohistochemical and molecular techniques.
- a. All patients will have a pre-treatment biopsy specimen. Adequacy of the biopsy specimen for laboratory investigation will not be a criterion for inclusion or exclusion from the study.
  - b. For those patients who have an adequate biopsy specimen, the characteristics of the specimen will be analyzed and matched with treatment outcome.
  - c. For patients who undergo surgery following initiation of vismodegib treatment - failure (outcome #1) or intolerance of side effect (outcome #3) - the pre- and post-treatment characteristics of the tumor within the surgical specimens will be analyzed and compared.

- d. All patients will have blood drawn at initiation of therapy and at 6 month intervals for 1 year or at time of early discontinuation of vismodegib. One 5 ml red top tube and two 10 ml purple top (EDTA) tubes will be drawn, in this order, for each interval. Blood will be drawn at the Kellogg Eye Center and processed in [name] laboratory. Serum and blood will be barcoded and stored in a -80 freezer for marker and genetic analysis and correlation with histo-pathologic findings.

See **Table 16** (Appendix 4) for a Schedule of Assessments.

### 3.2 Rationale for Study Design

**Hypothesis: Treatment of orbital and periocular BCCA with oral vismodegib facilitates globe-sparing treatment of orbital BCCA, and lacrimal apparatus-sparing treatment of medial canthal BCCA.**

This is a prospective study that will follow the interventional standard of care use of vismodegib in patients with locally advanced BCCA that threatens the globe or lacrimal drainage system (see flow chart), and utilize a laboratory approach to identify predictors of disease severity, progression and response to treatment.

### 3.3 Outcome Measures

**Primary Outcome Measure:**

Determined by analyzing visual function per **Table 15** at completion of the study. **A weighted score of at least 21 out of possible 50 would constitute a successful treatment outcome.**

**Secondary Outcome Measures:**

Visual function measures collected numerically at 3-month intervals will be correlated with size of tumor and timing of surgery (if any).

In addition, a laboratory basic research protocol will utilize histologic and molecular analyses of the tumors, as outlined below. **The aim of the basic research protocol is to characterize the tumor response to vismodegib treatment in order to determine the biology of tumor shrinkage/fibrosis, determine whether compensatory pro-oncogenic pathways are induced by treatment, and to identify potential markers that correlate with good treatment response.** The specific aims are:

- 1) **Aim 1:** Histologically assess the cellular characteristics and extent of residual tumor and its relationship to:
  - a. Vascular supply
  - b. Lymphatic vessels
  - c. Nerves
  - d. Leukocytes

*Hypothesis: the response to vismodegib is unevenly distributed, and is anatomically driven by the vascular bed, watershed zones, and the presence of tumor-clearing leukocytes.*

**Using histologic and immunohistochemical techniques, the tumor will be assessed from pre-treatment biopsy specimens as well as post-treatment specimens. Micro-anatomical techniques, including high-resolution tile scanning of multiple sections, and immunofluorescence techniques, will be used to develop a reproducible system that will measure capillary and tumor cell densities, to develop possible predictors of vismodegib resistance based on tumor anatomy. When possible (per tissue availability), transmission electron microscopy will be used to characterize the cellular and stromal response to vismodegib treatment.**

- 2) **Aim 2:** Develop a profile of biomarkers within the tumors before and after treatment.

*Hypothesis: inhibition of hedgehog signaling with vismodegib alters the biology of other signaling pathways, which can lead to opportunities for multi-modal treatment synergies for resistant tumors, as well as identify risk factors for resistant tumors.*

**Utilizing immunofluorescence and confocal microscopy techniques, each tumor will be profiled for expression of a comprehensive set of ligands and receptors of the above-mentioned pathways. Using laser microdissection**

(LMD) and quantitative PCR technology (qPCR), specific regions within tumors will be profiled and compared within and between tumors for expression of ligand-receptor pairs before and after vismodegib treatment, along with the presence of mutations within genes that are known to bypass or confer resistance to hedgehog pathway inhibition. Expression of cancer stem cell markers will also be assessed via qPCR, in both tumor and in blood samples from patients before and after vismodegib treatment, to identify possible serum markers for tumor sensitivity and response. Collaborators include [name], University of Michigan, and [name], Genentech, Inc.

### 3.4 Safety Plan

Patients will be evaluated at regular clinic visits for the duration of the study participation

Specific potential safety issues for this trial are outlined below.

Please refer to the Vismodegib Investigator Brochure for a detailed description of the safety profile of vismodegib.

See Section 5.1 (Assessment of Safety) for complete details of the safety evaluation for this study.

### 3.5 Compliance with Laws and Regulations

This study will be conducted in accordance with current U.S. Food and Drug Administration (FDA) Good Clinical Practices (GCPs), and local ethical and legal requirements.

## **EXCLUSION CRITERIA**

**Patients will be excluded from the study based on the following criteria:**

- Inability or unwillingness to swallow capsules
- Inability or unwillingness to comply with study procedures and protocol
- Pregnant, lactating or breast feeding women
- Women of childbearing potential.
- Uncontrolled medical illnesses
- Age under 18 years
- Dementia or significantly altered mental status that would prohibit the understanding or rendering of informed consent and compliance with the requirements of this protocol.

## 4.2 Method of Treatment Assignment

Treatment will be determined by the treating physicians in accordance with SOC. The PI will determine eligibility for the study and be the final arbiter for inclusion of patients. There will be no randomization.

## 4.3 Study Treatment

The study treatment will follow SOC protocol for BCCA that threatens the eye or lacrimal apparatus. The study aims to enroll 50 patients over 3 years and follow each patient for 1 year.

### Vismodegib Dosage

Vismodegib is 150 mg taken QD PO until disease progression or until unacceptable toxicity. Vismodegib may be taken with or without food.

- **Swallow capsules whole**
- **Do not open or crush capsules**
- **If a dose of vismodegib is missed, do not make up that dose; resume dosing with the next scheduled dose.**

### Vismodegib Dose and Schedule Modifications

Vismodegib dose modifications and schedule modifications during the study are not recommended due to the pharmacokinetic characteristics of the drug (see Vismodegib Investigator Brochure v9, Section 5.9.3). Briefly, vismodegib's pharmacokinetic profile is a result of high affinity, reversible binding to Alpha-1 acid Glycoprotein (AAG) and binding to albumin, in addition to solubility limited absorption and slow metabolic elimination properties (Graham 2011). Initiation of less frequent administration schedules than the approved dose and schedule of vismodegib of 150 mg orally once daily, (i.e. 150 mg three times weekly [TIW] or 150 mg once weekly [QW] dosing), was associated with marked decrease in the pharmacologically active unbound fraction.

Unbound steady-state vismodegib concentrations were 60% and 85% lower for the TIW and QW dose groups, respectively, relative to the QD dose group (LoRusso et al. 2011b). Such decreases may be associated with loss of vismodegib activity based on findings from nonclinical models. Integrated PK/pharmacodynamic modeling of vismodegib in xenograft models has revealed a steep relationship between pathway modulation (GLI1 inhibition) and anti-tumor effect, suggesting that even small reductions in exposure could lead to dramatic loss in vismodegib activity (see Vismodegib Investigator's Brochure v9, Section 4.1.2.8)

Dose reduction of vismodegib is not permitted as there is only a 150-mg capsule strength available. Capsules should not be opened or crushed. If

a treatment interruption occurs, and it is determined that vismodegib will be re-started, the original dose will be maintained

### **Vismodegib Overdosage**

There is no information on overdosage in humans. In clinical trials, ERIVEDGE capsule was administered at 540 mg QD; exposure did not increase between 150 mg and 540 mg daily.

### **Vismodegib Clinical Formulation and Storage**

For the clinical studies, hard gelatin capsules containing 150 mg vismodegib are available. The 150-mg vismodegib drug product is a hard gelatin capsule formulation for oral administration. The capsule fill consists of vismodegib and the following excipients: microcrystalline cellulose PH101, lactose monohydrate, sodium lauryl sulfate, povidone K29/32, sodium starch glycolate, talc, magnesium stearate, and purified water. All of these excipients are compendial (USP/NF-EP) grade. The capsule shell consists of gelatin, red iron oxide, black iron oxide, and titanium dioxide. A compendial-grade black printing ink may be used.

Vismodegib capsules should be stored in the recommended storage conditions at 15°C–30°C. Information on the shelf life of the capsules is provided on the label.

## **4.4 Concomitant and Excluded Therapy**

### **Drugs that Inhibit or Induce Drug Metabolizing Enzymes**

Vismodegib elimination involves multiple pathways. Vismodegib is predominantly excreted as an unchanged drug. Several minor metabolites are produced by multiple CYP enzymes. Although vismodegib is a substrate of CYP2C9 and CYP3A4 *in vitro*, CYP inhibition is not predicted to alter vismodegib systemic exposure since similar steady-state plasma vismodegib concentrations were observed in patients in clinical trials concomitantly treated with CYP3A4 inducers (i.e., carbamazepine, modafinil, and phenobarbital) and those concomitantly treated with CYP3A4 inhibitors (i.e., erythromycin and, fluconazole).

### **Drugs that Inhibit Drug Transport Systems**

*In vitro* studies indicate that vismodegib is a substrate of the efflux transporter P-glycoprotein (P-gp). When ERIVEDGE is coadministered with drugs that inhibit P-gp (e.g. clarithromycin, erythromycin, azithromycin), systemic exposure of vismodegib and incidence of AE of ERIVEDGE may be increased.

### **Drugs that Affect Gastric pH**

Drugs that alter the pH of the upper gastrointestinal (GI) tract (e.g., proton pump inhibitors, H2-receptor antagonists, antacids) may alter the solubility

of vismodegib and reduce its bioavailability. However, no formal clinical study has been conducted to evaluate the effect of gastric pH altering agents on the systemic exposure of vismodegib. Increasing the dose of ERIVEDGE when coadministered with such agents is not likely to compensate for the loss of exposure. When ERIVEDGE is coadministered with a proton pump inhibitor, H2-receptor antagonist or antacid, systemic exposure of vismodegib may be decreased and the effect on efficacy of ERIVEDGE is unknown.

#### **Effects of Vismodegib on Other Drugs**

Results of a drug-drug interaction study conducted in cancer patients demonstrated that the systemic exposure of rosiglitazone (a CYP2C8 substrate) or oral contraceptives (ethinyl estradiol and norethindrone) is not altered when either drug is co-administered with vismodegib.

In vitro studies indicate that vismodegib is an inhibitor of CYP2C8, CYP2C9, CYP2C19 and the transporter BCRP. Vismodegib does not induce CYP1A2, CYP2B6, or CYP3A4/5 in human hepatocytes.

## **4.5 Study Assessments**

### **Assessments during Treatment**

- **Pregnancy test:** All women of childbearing potential (including those who have had a tubal ligation) will be excluded from this study. This will have no bearing on their eligibility for treatment with vismodegib per SOC by their treating physician.

### **Ophthalmologic Exam Follow-Up Assessments**

At month 3 and every 3 months a standard oculo-plastic eye exam to assess visual function (see Table 15). The tumor size will be measured in two coordinates using a metric ruler at each clinic visit. This will be performed by the treating physician or a trained designee.

MRI or CT with contrast and clinical photographs will be obtained prior to the onset of treatment (per SOC). Clinical photographs will be obtained at subsequent clinic visits (every 3 months), and a follow up MRI or CT will be obtained at 5 and 9-12 months (+/- 1 month) after initiation of vismodegib therapy to assess tumor response/progression, and additionally at the discretion of the treating physician (per SOC).

**Progression of disease**, per ophthalmic/oculo-plastic evaluation, will result in offering the patient a surgical approach. Patients will continue to be followed for the duration of the study period irrespective of vismodegib treatment status. If progression of disease is suspected by the Medical Oncology team, then an urgent ophthalmic evaluation will be obtained within 2 weeks or less.

Patients will be followed for 1 year after initiation of vismodegib treatment, or 1 month (+/- 1 month) following surgery.

#### **4.6 Discontinuation of Protocol-Specified Therapy**

Protocol-specified therapy may be discontinued for any of the following reasons:

- Patient election to discontinue study participation (for any reason)
- Patient election to refuse treatment (for any reason)
- Treating physician's judgment

#### **4.7 Subject Discontinuation**

All subjects who enroll in the study will be followed for 1 year, -1/+3 months, at which point their study participation will be deemed completed. If patients undergo tumor resection surgery prior to completion of the study, they will be given their final study evaluation within 1 month after the surgery, at which time their enrollment will be deemed completed. Subjects who discontinue vismodegib prior to the end of the 1-year study period, do not restart vismodegib within 30 days, and refuse surgery, will be deemed to have completed the study and their evaluation within 1 month of treatment discontinuation will be considered their exit time point and primary end point. Subjects who decide to resume vismodegib will be able to reenroll to complete the 1-year trial period.

Subjects who discontinue vismodegib before completing the 1-year study will return for evaluation by Ophthalmology within the first month post-operatively, at which point the final evaluation will be completed and their study enrollment will be deemed complete.

Completion of a final Ophthalmology evaluation and Visual Assessment Score will constitute a subject's completion of the study if so deemed by the PI.

See Table 16.

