## **OUTCOME ASSESSMENT**

- 8) The **PRIMARY OUTCOME** will be determined by analyzing visual function per **Table 15** at 1 year following initiation of vismodegib treatment or at 2 months +/- 1 month following surgery, whichever is longer (i.e. final assessment may be extended up to 15 months following initiation of vismodegib). **A weighted score of at least 21 out of possible 50 would constitute a successful treatment outcome.**

- 9) **SECONDARY OUTCOMES will be assessed via subgroup analysis:**
- a. If the tumor progresses (PD) while on vismodegib treatment, then treating physician may discontinue vismodegib and offer surgical resection or debulking per SOC → **OUTCOME #1 (Progressive Disease)**.
  - b. If patient refuses surgical option, then continue monitoring patient.
  - c. Patients with stable or shrinking tumors (CR, PR or SD) will be considered “**Responders**.”
  - d. If the tumor responds within the first year of treatment and patient tolerates side effects (per patient), CONTINUE vismodegib therapy and monitoring until the end of the study → **OUTCOME #2 (SD, PR or CR and good tolerance)**
  - e. If patient reports subjectively intolerable side effects (per patient), then discontinue vismodegib, and treating physician can offer surgical resection or debulking → **OUTCOME #3 (SD, PR or CR and poor tolerance)**.
  - f. If patient refuses surgical options, continue monitoring.
  - g. A treatment break, or “drug holiday” will not be offered as an option as part of this study.
  - h. If treatment with vismodegib is stopped but the patient later decides to restart vismodegib, then the patient’s exam findings at termination of treatment will be used for assessing the primary outcome. The patient can continue to be followed as part of the study, and additional exam findings can be used for secondary outcome assessment.

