### **EVALUATION**

- 10) VA, diplopia, motility, and tearing are assessed at each office visit (Visual Assessment Weighted Score see **Table 15**).
- 11) Patients undergoing surgery will have their specimen assessed histologically for the presence of tumor, and used for comparison to baseline biopsy.
  - a. The presence of tumor at the surgical margin will be determined by the pathologist. Absence of tumor at the surgical margin will lead to a presumptive cure.
- 12) The **primary outcome** will be the Visual Assessment Weighted Score (Table 15) at 1 year following initiation of vismodegib or 2 (+/- 1) months after tumor excision/debulking surgery, whichever is longer.

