**Table 16: Schedule of Assessments**

	Screen	Initiation of Vismodegib	Assessments (+/- 1 month  )											12, -1/ +3 months (or 1 month post-op following surgery) 	Withdrawal of vismodegib for surgical treatment (+/- 1 month)	Early withdrawal of vismodegib		
			1	2	3	4	5	6	7	8	9	10	11					
Study Visit (months)																		
Informed Consent	x																	
Demographics	x																	
Medical History 	x																	
Medical Exam 	x	x	x		x 			X 			X 			X 		X 	X 	
Ophthalmic oculoplastic exam 	x				x			x			X			x		x	x	
Standard clinical photos	x				x			x			x			x		x	x	
Visual Assessment Score (pre) 	x																	
Visual Assessment Score (post) 					x			x			x			x		x	x	
Biopsy for histologic diagnoses/evaluation	x																	
MRI or CT scan 	x							x						X 		x	X 	X 
CBC/Chemistry Labs 	x				x			x			x			x		x	x	x
Biomarker Draw	x							x						x		x	x	x
Response Evaluation 					x			x			x			x		x	x	x
AE assessment 		x	x	x	x	x	x	x	x	x	x	x	x	x	x	x	x	x

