## Footnotes:

1. Medical history including smoking history. Assessed by Ophthalmology team.
2. Medical exam assessed by Med Onc team. 3 month supply of medication will be provided at the time of each standard 3-month visit.
3. Ophthalmic exam should include visual acuity, slit lamp exam, eye motility and tearing. Assessed by Ophthalmology team.
4. See Table 14 in the protocol. Assessed by Ophthalmology team.
5. See Table 15 in the protocol. Assessed by Ophthalmology team.
6. Additional MRI/CT will be for tumor measurements and assessments. Assessed by Ophthalmology team.
7. CBC/Chemistry lab tests per Med-Onc team for SOC.
8. Assessed by Ophthalmology team.
9. Assessed by Med-Onc team.
10. Visits may be scheduled more frequently per Med-Onc or Ophthalmology team discretion. Last medical exam will occur prior to surgery. Remaining medication and diary should be returned to Ophthalmology.
11. Per the discretion of the Ophthalmologist.
12. Subjects will be followed for 1 year or until surgery followed by one month post-operative evaluation.
13. 9-12 month window for CT-MRI imaging, as determined by the treating physician.

## APPENDIX 5

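### For patients operated on before about month 10, the protocol gives incompatible times for reading the primary visual score, and no text says which rule governs

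*Combined protocol and SAP*

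**What the plan says.** Section 3.1, Outcome Assessment, item 8, determines the primary outcome "at 1 year following initiation of vismodegib treatment or at 2 months +/- 1 month following surgery, whichever is longer", and adds that the last assessment may fall as late as 15 months after initiation. Item 12 under Evaluation repeats the rule: "at 1 year following initiation of vismodegib or 2 (+/- 1) months after tumor excision/debulking surgery, whichever is longer".

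Other sections time the end of the study differently for operated patients:

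- Section 4.7: "they will be given their final study evaluation within 1 month after the surgery, at which time their enrollment will be deemed completed".
- Section 4.5, Ophthalmologic Exam Follow-Up Assessments: "Patients will be followed for 1 year after initiation of vismodegib treatment, or 1 month (+/- 1 month) following surgery".
- Appendix 4, Table 16, final-visit column: month 12 (-1/+3), "or 1 month post-op following surgery". Footnote 12: "Subjects will be followed for 1 year or until surgery followed by one month post-operative evaluation".

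For patients who stop the drug, do not restart within 30 days and decline surgery, 4.7 says "their evaluation within 1 month of treatment discontinuation will be considered their exit time point and primary end point" and treats them as having completed the study. Section 4.5 says "Patients will continue to be followed for the duration of the study period irrespective of vismodegib treatment status", and items 9b and 9f of 3.1 call for continued monitoring when surgery is refused.

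For patients who stop and later restart, item 9h takes the primary reading at termination of treatment and assigns later findings to the secondary outcomes. Section 4.7 lets such patients enroll again to finish the year.

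Section 3.3 places the primary reading at study completion. Section 4.9 names no time point for the primary test and no order of precedence.

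**The concern.** The trial has one arm and one primary test, on a single proportion: the share of enrollees who score at least 21 of 50 points. That proportion is defined only if each patient has one reading time. For an operated patient, one part of the protocol requires a reading at month 12 or later, while another ends participation about a month after the operation.

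Two things are at stake. If both scores exist, the choice between them could be made in an open-label study after the outcomes are known. If sites follow 4.7, the month-12 score that items 8 and 12 require may never be collected, and no analysis can recover it. Early exit is evidently meant to operate: item 4c of 3.1 cites 4.7 when it excuses early completers from further medical oncology exams.

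**Working it through.** **Inputs.** Let s be the month of surgery, counted from initiation.

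- Items 8 and 12: nominal time A(s) = max(12, s + 2). The post-operative window is 1 to 3 months. These items give no window around one year, so the -1 month allowance of 4.7 and Table 16 is granted here. The earliest acceptable visit is then max(11, s + 1).
- Section 4.7: latest time B(s) = s + 1.
- Section 4.5: s to s + 2, or month 12. It does not say whether the earlier or the later applies.
- Section 4.9: n = 50, null rate 0.30, alternative 0.50, one-sided exact binomial test at 0.05.

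**Gap in operated patients, A(s) − B(s).**

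- s = 1: 12 − 2 = 10 months
- s = 3: 12 − 4 = 8 months
- s = 6: 12 − 7 = 5 months
- s = 9: 12 − 10 = 2 months

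**Can one visit satisfy both rules?** This needs s + 1 ≥ max(11, s + 1), that is s ≥ 10. For surgery before month 10 it cannot, even with the -1 month window. From month 10 on, a visit exactly one month after surgery meets both.

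**Example.** Surgery at month 4: items 8 and 12 give month 12, 4.7 gives month 4 to 5, and Table 16 gives month 5 (or 12).

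**Patients who stop and decline surgery.** For stopping at month t, the 4.7 reading precedes month 12 by at least 12 − (t + 1) months: 10, 8, 5 and 2 for t = 1, 3, 6 and 9. Whether this is a contradiction depends on whether 4.7 is meant as an exception.

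**Does other text settle it?** Section 3.3 refers to study completion, but 4.7 defines completion by patient path and leaves it partly to the principal investigator's judgment. So 3.3 leads back to 4.7 and does not reconcile it with items 8 and 12. The Missing Data text in 4.9 says how incomplete data are to be filled in, not which time applies.

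**Sensitivity of the test.** The stated power reproduces. With n = 50 the smallest number of successful patients with type I error at or below 0.05 is 21: P(X ≥ 21 | 0.30) = 0.0478 and P(X ≥ 21 | 0.50) = 0.8987, against the stated 90%. At 20 successes, P(X ≥ 20 | 0.30) = 0.0848. One patient moved from success to failure at the boundary therefore changes the conclusion. (This count of 21 patients is separate from the 21-point score threshold.)

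**The case against.** The strongest reply is that much of this can be read coherently. For those who stop and decline surgery, 4.7 is an express subgroup rule, and such a rule is ordinarily read as qualifying a general one. The opposing text in 4.5 and items 9b and 9f concerns follow-up and does not name the primary reading. This has force, so that limb is secondary. It does not remove the conflict over whether these patients leave the study or stay in it.

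The same reply fails for operated patients. Items 8 and 12 already address surgery and choose the later time, so 4.7 does not fill a gap there.

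A second reply is that a site following 4.7 will hold only one final score, which 3.3 then selects. That is partly right: the defect is as much one of conduct as of analysis. But the score then selected is not the one items 8 and 12 define.

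A third reply is that success may not change with timing. An intact globe gives 20 of the 21 points needed, and any one further item met in full adds at least 2. A globe lost at the operation is already counted at the early post-operative visit, and patients who decline surgery lose those points only if they later have such surgery. This stands.

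A reader might also infer that restarters have no defined primary reading. Item 9h gives them one; only the re-enrollment sentence in 4.7 needs aligning with it.

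**Conclusion.** The timing of the primary endpoint is contradictory for patients operated on before month 10, by about 10 months at the extreme (surgery at month 1), and nothing in the protocol sets precedence. For those who stop the drug and decline surgery, precedence is unstated but an exception is a fair reading. Patients who stay on the drug for the year without surgery have a consistent month-12 reading.

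It is tempting to conclude that early readings inflate the success rate. The documents do not support that. An early reading could miss a later globe loss, but other scored items can recover with time, so neither the size nor the direction of a bias can be computed, and it may be zero. Nor do the drug-stopping rates quoted in section 1.3 for other vismodegib studies measure how many patients are affected: they are not rates of early surgery or of refusing it, and the populations and follow-up differ. The stated 90% power is not in dispute.

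The finding rests on the endpoint being undefined for some patients, together with a test whose conclusion can turn on one patient at the boundary. It should be corrected before the data are analysed.

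**What to change.** State one primary reading time for each patient path (on drug for the year, operated, stopped without surgery, restarted), timed from first initiation and fixed before analysis. Align items 8, 9h and 12 of 3.1, sections 3.3, 4.5, 4.7 and 4.9, and Table 16 with footnote 12 to that statement.

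- If the later-of rule in items 8 and 12 is kept, retain the month-12 eye visit for operated and stopped patients, and use the early post-operative or discontinuation score in a sensitivity analysis.
- If early readings are intended for some groups, say so once and do not describe the result as a one-year rate.
- In either case, state that re-enrollment creates no second primary record.

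The cost is a protocol amendment and, under the first option, a month-12 eye visit for some patients, a visit type already in Table 16. Some of these patients may not return. The change concerns only when the outcome is read; no treatment rule changes.
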